Surgery and dismissal: Participants will be randomized 1:1 to one of the 2 groups upon dismissal from the hospital after bilateral oophorectomy: standard dose estradiol, (including dosing dictated by personal medical history) or titrated dose estradiol therapy. Women with an intact uterus will also be prescribed a progestogen for endometrial protection. The preferred progestogen will be oral micronized progesterone, given as oral dose 100 mg daily or 200 mg cyclically during the first 12 days of month. Women belonging to the titrated dose ET group will initially be dismissed on the standard 100 mcg transdermal estradiol patch. They will have their estradiol levels checked once every 3-4 weeks (clinical visits overseen by our MD investigators in the Menopause and Women's Sexual Health Clinic) and the estradiol dose accordingly titrated until they reach the desired goal of an estradiol level of 80-120 pg/ml. If women in the standard dose group report residual symptoms despite treatment, we will offer titration to a higher dose of ET. Women intolerant of the estradiol patch will be treated with oral estradiol at an equivalent dose. Women with intolerance/side-effects/abnormal uterine bleeding with progesterone will be offered an alternative progestogen for uterine protection. Clinical care of the subjects will be overseen by clinical care providers in the Menopause and Women's Sexual Health Clinic.

The study is designed to have active study participants on varying hormone replacement after oophorectomy as dictated by their clinical needs.

Post-operative Study Visit at 6 Months: The same protocol will be followed as the baseline study day protocol above except we will not check glucose, lipids and insulin levels, and DXA scan will not be performed, as it will take longer than 6 months to see changes in these measures. Blood samples drawn for levels of estradiol and estrone will ideally be drawn on the second day after application of a new patch.

Post-operative Study Visit at 12 Months: Subjects will report to the clinical research and trials unit (CRTU), and the same protocol will be followed as that of the baseline study day visit. All blood samples will be drawn in

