the same way as done for the baseline visit. A 24-hour urine sample will be collected again in a mail-in kit as described above. Participants on any kind of exogenous glucocorticoid therapy will be excluded from this part of the study. Urine samples will be aliquoted and stored as a part of the IRB # 13-005838 biobank. Urine steroid profiling will be performed in batches in the ICL lab.

Time controls will complete baseline, 6 month, and 12 month study visits.

Participant Retention: All participants will be remunerated up to \$300. Participants will be remunerated \$100 for each of the following visits: baseline, six months and twelve months. If a participant refuse the cardiovascular testing, and chooses the option to complete the blood-work, questionnaires and DXA scan only, they will be remunerated \$50 for each of the following visits: baseline, six months and twelve months. Amounts will be prorated according to the visits the participant completes. In addition, participants will be provided with Mayo parking vouchers for the time they are onsite for study visits. For CRTU visits, participants will be given six-hour vouchers, and for other visits participants would be given 2 hour parking vouchers. After the long visits in the CRTU, which requires fasting for 8 hours, participants will be provided a meal.

Statistics (prepared in collaboration with [name], Ph.D.): For the proposed investigation, women 21-45 years of age undergoing bilateral oophorectomy will be randomized to one of two groups, based on the regimen of estradiol replacement therapy (standard versus titrated). In addition to estradiol, patients who do not undergo hysterectomy will receive a progestogen as clinically indicated. A randomization schedule will be generated by the Section of Biostatistics using varied blocked randomization to attain an equal number of women assigned to each treatment group. Covariates not balanced through randomization, such as additional hormone use in patients with hysterectomy, will be accounted for in analysis. For all aims, the primary analyses will be performed using intention to treat with **estradiol dosing regimen** as the *treatment group variable* and secondary analyses will be performed using the **serum estradiol concentration (E2)** as a *continuous explanatory variable*.

Statistical Analysis:

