Aims 1 and 3: We will first perform cluster analysis among the variables to identify set of variables that are highly correlated, and regression analysis to identify the dependency between the outcome variable and its covariate. We will also perform a multivariable regression analysis taking into account all the covariates and applying penalized methods such as least absolute shrinkage selection operator (lasso) [17] for covariate selection.

Aim 2: We will plot the data to identify the patterns between the outcome variable and the covariates. We will then fit a mixed-effects model with two fixed effects parameters, the intercept and the slope of the linear trend for the population, and two random effects for each participant, i.e., the deviations in intercept and slope of that participant's time trend from the population values.

Power calculation: The analysis of the 12 month outcomes will be considered the primary analysis, with analyses of the earlier time point used to supplement the primary findings. In all cases, distributional assumptions will be assessed with transformations or non-parametric methods used as appropriate. When the direction of a difference is hypothesized a priori (e.g. women receiving the lower dose of estradiol will have poorer endothelial vasodilator function) a one-tailed test will be used; if the direction is not stated a two-tailed test will be used.

Sample-size/statistical power considerations: In general, a sample-size of N=25 per group will provide statistical power (one-tailed, alpha=0.05) of 82% to detect a difference between groups of 0.75 standard deviation units. Therefore, although preliminary data are not available for each aim and the statistical power will differ for the multiple facets of each aim, we believe that a sample-size of N=25 per group will provide adequate statistical power to test both our primary and secondary hypotheses.

Investigative Sequence and Timeline:

Year	Aims	Number of Studies (Total = 150)
1	1 and 2	~50 (~15-18 participants and 3 visits each)
2	1 and 2	~50 (~15-18 participants and 3 visits each)
3	1 and 2	~50 (~15-18 participants and 3 visits each)

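### Covariates for the regimen comparison are not limited to values fixed before randomisation, so adjustment could remove or distort part of the effect in Aims 1 and 3

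*Combined protocol and SAP*

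**What the plan says.** The Statistics section sets the primary analyses for all aims as intention to treat, with the assigned dosing regimen as the group variable. Serum estradiol is the explanatory variable in the secondary analyses. The adjustment rule is: "Covariates not balanced through randomization, such as additional hormone use in patients with hysterectomy, will be accounted for in analysis".

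Under Statistical Analysis, Aims 1 and 3 are given clustering of variables, regression, and a "multivariable regression analysis taking into account all the covariates" with lasso selection. No covariate list appears, and nothing confines covariates to baseline.

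On timing, the Surgery and dismissal section states: "Participants will be randomized 1:1 to one of the 2 groups upon dismissal from the hospital after bilateral oophorectomy". The same section allows hormone treatment to change afterwards. A higher estradiol dose may be offered for residual symptoms in the standard arm, and: "Women with intolerance/side-effects/abnormal uterine bleeding with progesterone will be offered an alternative progestogen for uterine protection".

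Hormone levels and questionnaires are repeated at 6 and 12 months. The 12-month outcomes are primary.

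**The concern.** An intention-to-treat effect keeps the protection of randomisation only if the adjustment variables cannot have been changed by the assignment. Imbalance in a pre-randomisation variable is chance. Imbalance in an on-study variable may be the regimen at work.

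The two rules together tend to pick the wrong kind of variable. A trigger based on imbalance favours variables that differ between arms, and lasso favours variables that predict the outcome. A variable through which the regimen acts does both. The one example in the plan is also worded as hormone use, which can change during the study, and not as uterine status, which cannot.

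At stake is what the Aim 1 and Aim 3 estimates mean. After adjustment for a consequence of the regimen, the coefficient is no longer the total effect of assignment.

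**Working it through.** **1. The plan's own figure.** Inputs from the sample-size paragraph: "a sample-size of N=25 per group", one-tailed alpha 0.05, difference 0.75 SD, stated power 82%.

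- Standard error = √(2/25) = 0.283 SD.
- Noncentrality = 0.75/0.283 = 2.65, with 48 degrees of freedom and critical t = 1.677.
- Power = 83.4%, which agrees with the stated figure to within 2 points. The two-sided t-test gives 73.8% and does not match.

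The stated calculation contains no covariate, so this point leaves it unchanged.

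**2. Which variables are fixed at randomisation.**

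| Variable | Fixed before dismissal? | Can the regimen affect it? |
|---|---|---|
| Age, pre-surgery outcome value | Yes | No |
| Uterine status, hence the initial progestogen indication | Yes | No |
| Progestogen switch or stop, other hormone use | No | Possibly |
| Estradiol dose increase | No | Yes; the symptom-driven offer is written for the standard arm, and the other arm is titrated to level |
| Estradiol, estrone, symptoms, sleep or activity at 6 or 12 months | No | Possibly |

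The plan's wording does not separate the first two rows from the last three.

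**3. Size under assumed scenarios.** The documents give no rates of on-study hormone use and no effect of such use on the outcomes. Every scenario input below is therefore an assumption. The total effect is 0.75 SD with 25 per arm, one-tailed 5%.

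*Binary variable*, used by proportions p₀ and p₁ of the two arms and shifting the outcome by c SD: adjusted effect = 0.75 − c(p₁ − p₀). The standard error is 0.283 × √VIF, where VIF = 1 + (p₁ − p₀)²/(4v) and v is the mean within-arm variance of use.

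- 30% v 30%, c = 0.5: 0.75 − 0 = 0.75 SD; no loss.
- 20% v 50%, c = 0.5: 0.75 − 0.15 = 0.60 SD; v = 0.205, VIF = 1.11, standard error 0.298, noncentrality 2.01, power 63% (simulated 62%, against 81% unadjusted).
- 20% v 70%, c = 0.5: 0.75 − 0.25 = 0.50 SD; v = 0.185, VIF = 1.34, standard error 0.327, noncentrality 1.53, power about 44% (simulated 44%, against 82% unadjusted).

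*Continuous variable* differing by m SD between arms and carrying a share f of the effect: adjusted effect = 0.75(1 − f), VIF = 1 + m²/4, residual variance 1 − g² with g = 0.75f/m.

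- f = 0.5, m = 1.0: 0.375 SD; standard error √(0.08 × 1.25 × 0.859) = 0.293, power 35% (simulated 36%).
- f = 0.5, m = 1.5: 0.375 SD; standard error √(0.08 × 1.5625 × 0.9375) = 0.342, power 29% (simulated 28%).

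Simulations used 4,000 to 6,000 trials per setting. These scenarios all attenuate, but the direction is not guaranteed. Reversing the sign of c in the 20% v 50% case gives 0.75 + 0.15 = 0.90 SD.

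**4. After the fix.** With progestogen use determined by uterine status, assumed to be 50% in both arms, the simulated estimate was 0.74 SD and power about 82%, with or without adjustment.

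**The case against.** The strongest reply is that the named covariate is in effect a baseline factor. Progestogen goes to women with a uterus in either arm, uterine status is settled at surgery, and randomisation follows "upon dismissal from the hospital after bilateral oophorectomy". The Limitations section says that the progestogen might influence the measurements, which fits adjusting for a prognostic factor unbalanced by chance. This stands for the initial indication. It does not cover later changes in use. On its literal wording the example concerns women with hysterectomy, while the sentence before it gives progestogen to those who do not have one. Until the two are reconciled, the reader cannot tell which variable is meant.

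Three further replies also stand in part:

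- Serum estradiol is assigned to the secondary analyses. That does not bar it from the lasso model, and it says nothing about dose, estrone or symptoms.
- The lasso regression is introduced as an additional analysis and is not shown to be the primary comparison. The adjustment rule in the Statistics section stands apart from it, however, and no other model is specified for the regimen comparison in Aims 1 and 3.
- The progestogen provision offers an alternative product, so a yes/no indicator might not change, and no section says that bleeding or intolerance differs by regimen. That link is a possibility only.

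A reader might infer that the plan intends to adjust for on-treatment values, or that the regimen effect will shrink. The documents support neither. They never list estrone, symptoms or similar measures as covariates, and many of these are also measured at baseline and could enter as baseline values.

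**Conclusion.** The point holds as a missing restriction combined with a selection rule that works in the wrong direction. The plan permits variables arising after randomisation to enter the Aim 1 and Aim 3 regimen comparison; it does not commit to using them. Bias arises only if an adjusted variable is affected by the assigned regimen.

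The size cannot be found from the documents. It ranges from nothing, when use is unrelated to arm, to about half of a 0.75 SD effect with power of 28-36%, under assumed mediation of one half and an assumed arm difference of 1.0 to 1.5 SD in the adjusted variable. These figures illustrate sensitivity and do not forecast this trial.

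**What to change.** In the Statistics section and under Statistical Analysis for Aims 1 and 3:

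- Replace the imbalance-triggered rule with a short fixed list of covariates known before randomisation for the primary comparison, for example the baseline value of the outcome, age, and uterine status at randomisation.
- Use uterine status in place of additional hormone use.
- Keep the regimen term unpenalised in any lasso model.
- Confine models containing on-study hormone use, dose, achieved estradiol or estrone, or any other 6- or 12-month measurement to analyses labelled secondary or exploratory.
- Define baseline explicitly. The DXA item of the Baseline Study Day Protocol lets limited-participation women have the baseline scan up to a month after oophorectomy, which may fall after randomisation and bears on Aim 3.
- Reconcile the reference to patients with hysterectomy with the preceding sentence on who receives a progestogen.

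The cost is a few sentences. The suggested covariates are already available, and neither the sample size nor the stated power calculation changes.

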
Aim 1: Compare the cardiovascular function in young women (<46 years) following bilateral oophorectomy who are treated with either the standard dose of estradiol(100 mcg or lower transdermal patch or equivalent oral dose) or titrated estradiol dosing to achieve average premenopausal estradiol level (80-120 pg/ml).

Hypothesis: Women receiving the titrated dosing of estradiol will have better cardiovascular function than women receiving the standard dose of estradiol.

Aim 2: Characterize the relationship between the serum estradiol level and cardiovascular function in young women (<46 years) on estradiol replacement after bilateral oophorectomy.

Hypothesis: There will be a dose response relationship between the serum estradiol level and cardiovascular function.

Aim 3: Compare the body composition in young women following bilateral oophorectomy who are treated with either the standard dose of estradiol (100 mcg or lower transdermal patch or equivalent oral dose) or titrated estradiol dosing to achieve average premenopausal estradiol level (80-120 pg/ml).

Hypothesis: Women receiving the titrated dosing of estradiol will have a body composition closer to their premenopausal state as compared to women receiving the standard dose of estradiol.

Background and Significance: Bilateral oophorectomy performed before the natural age of menopause is an important cause of premature estrogen deprivation, and may not be avoidable in women undergoing surgery for gynecologic cancer or ovarian cancer risk reduction in high risk individuals, such as BRCA mutation carriers.[6] In the absence of estrogen replacement therapy, these women are at increased risk for several adverse health outcomes including CVD, cognitive dysfunction, mood disorders, osteoporosis, accelerated aging and early death. The risk for many of these conditions is higher with younger age at oophorectomy.[6] Many professional societies, therefore, support the use of estrogen therapy for these women, not only for management of menopausal symptoms, but also to mitigate the adverse long-term health consequences of bilateral oophorectomy.[8, 9] The current clinical practice is to use estrogen-based hormone therapy at least until the natural age of menopause unless there is a contraindication to its use.[1] However, in the absence of evidence regarding the impact of the specific estrogen therapy regimens on health outcomes in these women,[10]

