treatment is usually tailored to symptom control. The general practice is to **use a dose of estrogen higher than that used for vasomotor symptom treatment in women after natural menopause** in order to approximate the physiologic estradiol levels in premenopausal women.[11] A transdermal estradiol patch delivering 100 mcg per day or lower, or its equivalent oral dose (2 mg per day), is commonly recommended for these young women.[12] However, this choice is not based on rigorous scientific evidence. While this approach serves to alleviate vasomotor symptoms in most cases, it is currently unknown if this dose is an effective strategy to prevent long-term adverse health consequences of early estrogen deprivation, and if an individualized treatment approach may result in better long-term health outcomes. Additionally, estradiol absorption and metabolism can be highly variable, accounting for differences in estradiol levels among women on identical estradiol dosing. **The current clinical practice is to titrate the estradiol dose to symptom control, and not to achieve the average premenopausal estradiol level of 80-120 pg/ml. It is reasonable to speculate that ET in young women with premature estrogen deprivation should be individualized and titrated to estradiol level in order to optimize their long-term health outcomes.**

This novel study has been designed to test hypotheses relevant to the health of a group of **understudied young women** at risk for increased mortality and numerous adverse long-term health outcomes. We are proposing to study the trends CVD risk markers between young women with bilateral oophorectomy who are treated with standard-dose estradiol therapy versus those whose estradiol dose is titrated to achieve the average premenopausal estradiol level (80-120 pg/ml). The CVD risk parameters that will be studied in the current protocol include arterial stiffness and cardiovascular response to sympathoexcitatory stressors.

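### Aim 2 and the secondary analyses relate outcome to a post-randomisation estradiol level with no named confounders, so a dose response could appear without any estradiol effect

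*Combined protocol and SAP*

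**What the plan says.** The Statistics section ranks two kinds of analysis. The lead one is by randomised arm: "For all aims, the primary analyses will be performed using intention to treat with estradiol dosing regimen as the *treatment group variable". Below it, "secondary analyses will be performed using the serum estradiol concentration (E2) as a *continuous explanatory variable".

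Aim 2 (Specific aims) is about the level itself: "Characterize the relationship between the serum estradiol level and cardiovascular function in young women (<46 years) on estradiol replacement after bilateral oophorectomy". Its hypothesis reads: "There will be a dose response relationship between the serum estradiol level and cardiovascular function". The Statistical Analysis section gives Aim 2 a "mixed-effects model with two fixed effects parameters, the intercept and the slope of the linear trend for the population", plus a random intercept and slope for each participant. It lists no regimen term and no covariates for this aim.

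Three other statements bear on what determines a woman's level:

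- Background and Significance: "estradiol absorption and metabolism can be highly variable, accounting for differences in estradiol levels among women on identical estradiol dosing".
- Surgery and dismissal, on the standard arm: "standard dose estradiol, (including dosing dictated by personal medical history".
- Same section: "If women in the standard dose group report residual symptoms despite treatment, we will offer titration to a higher dose of ET".

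The titrated arm is steered to 80-120 pg/ml. Confounding is addressed only in general terms. The Statistics section promises to account for covariates left unbalanced by randomisation, with additional hormone use as its one example. Multivariable regression with lasso selection is planned for Aims 1 and 3.

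**The concern.** Randomisation protects the comparison of regimens. It does not protect a comparison of women by the level they happened to reach. Within an arm, the level reflects how a woman absorbs and clears estradiol, which route she uses, her history, and whether symptoms led to a dose change. Any of these may also relate to arterial stiffness, sympathetic response or body composition.

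Because the titrated arm is held in a narrow band, much of the spread in level is likely to be this non-randomised spread in the standard arm. A single slope over all treated women blends it with the randomised shift between arms. At stake is the reading of Aim 2: a slope produced by a shared cause would be reported as a dose response. The Future plans section describes the study as pilot data for a larger trial of estradiol-targeted therapy, so that reading could carry forward.

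**Working it through.** **The plan's own figure.** For the randomised comparison the plan states 82% power with 25 per group, a difference of 0.75 SD and one-tailed alpha 0.05. Noncentral t: noncentrality 0.75 × √(25/2) = 2.65, df 48, critical value 1.677, power 83.4%. The figure reproduces to within 2 points. It concerns the regimen contrast; the plan gives no corresponding figure for the estradiol-level analyses.

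**Inputs for the illustration.** From the documents: 25 per arm and a titration target of 80-120 pg/ml. Assumed, because the documents give no estradiol distribution by arm and no strength of confounding: standard arm mean 70, SD 40; titrated arm mean 100, SD 12 pg/ml; a common cause with correlation *a* to level (within arm) and to outcome; no effect of estradiol; one measurement per woman.

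**Step 1: where the spread in level comes from.** Pooled variance = (40² + 12²)/2 + 30²/4 = 872 + 225 = 1,097, so SD = 33.1. The randomised gap contributes 225/1,097 = 21%. Spread within the standard arm contributes 800/1,097 = 73%.

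**Step 2: spurious correlation.** The average within-arm covariance is *a*² × (40 + 12)/2 = 26*a*², so pooled r = 26*a*²/33.1. Rejection by Fisher z with n = 50 uses shift = atanh(r) × √47.

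| *a* | r | shift | two-sided 5% | one-sided 5% |
|---|---|---|---|---|
| 0.3 | 0.071 | 0.49 | 8% | 12% |
| 0.4 | 0.126 | 0.87 | 14% | 22% |
| 0.5 | 0.196 | 1.36 | 28% | 39% |

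Simulation gives 8% / 14% / 27% two-sided. The regimen contrast in the same simulated data rejects in about 5%. With no common cause the pooled test also holds 5%, so the excess comes from confounding. The one-sided column matters only if the plan's one-tailed rule is applied to Aim 2, whose hypothesis does not state a direction.

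**Step 3: does a regimen term repair it?** No. It removes the randomised 225 and leaves the confounded part: r = 26 × 0.25/√872 = 0.22 at *a* = 0.5. False rejection rises to 33% by formula (34% in simulation).

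**Step 4: does the pre-surgery outcome help?** It does if the common cause already acts before surgery. Let ρ be the correlation of the outcome before and after surgery (assumed). With r = 0.196, the adjusted correlation is r(1 − ρ)/√[(1 − ρ²)(1 − r²)]:

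- ρ = 0.5: 0.116, rejection 12%
- ρ = 0.7: 0.084, rejection 9%
- ρ = 0.8: 0.067, rejection 7%

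A separate simulation with a stable outcome component and baseline adjustment alone took 27% down to 8%. A cause that first acts after surgery is not captured.

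**Step 5: regimen as instrument.** First-stage F = [gap/√((40² + 12²)/25)]² = (gap/8.35)². Gaps of 30 / 20 / 10 pg/ml give 12.9 / 5.7 / 1.4. The check also has little power. If a pooled correlation of 0.3 were wholly causal, gaps of 10 to 40 pg/ml (standard-arm SD 30 to 50) would imply regimen differences of 0.08 to 0.40 SD, for which 25 per group has 9% to 39% one-sided power.

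**The case against.** The strongest reply is that the randomised answer already leads. Regimen by intention to treat is primary for every aim, the level analyses are secondary, and the study calls itself a pilot. This stands, and it limits the point to Aim 2 and the secondary analyses. A reader might infer that the trial's case for a target level would rest on a confounded association. The documents do not support that: the Specific aims test whether titration to the target is superior to standard dosing, which is the randomised contrast.

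A reader might also infer that the plan openly pools the arms. No sentence says so. Pooling is inferred from the Aim 2 population (all women on replacement) and the absence of a regimen term. The Aim 2 slope is described as a time trend, so where estradiol enters that model is itself unspecified.

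The plan does have covariate provisions, and the Limitations section intends each woman to serve as her own control. The illustration uses one time point and no covariates, so it does not represent fully adjusted analyses for Aims 1 and 3. But the imbalance clause addresses chance differences between arms, which is a different problem, and lasso does not guarantee that a confounder is kept. Neither is stated for the Aim 2 model.

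Finally, one might expect the randomised arm, used as an instrument, to settle the matter. It cannot be relied on for that. The titrated arm starts on the 100 mcg patch and symptomatic women in the standard arm are offered higher doses, so the arms may separate little. Open-label treatment, with level checks every 3-4 weeks in one arm, strains the assumption that regimen acts only through estradiol level. A null regimen result would not refute an estradiol effect.

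**Conclusion.** The concern holds for Aim 2 and the secondary estradiol-level analyses, and leaves the primary test untouched. As specified, these analyses can show a dose response through confounding alone. In the illustration, false rejection is about 8% / 14% / 27% at common-cause correlations of 0.3 / 0.4 / 0.5, against a nominal 5%. Those rates depend on assumed estradiol distributions, assumed confounding and inferred pooling, and should not be read as predictions. The structural weakness depends on none of these values: the exposure is a post-randomisation level with acknowledged non-randomised causes, and the Aim 2 model names no adjustment for them.

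**What to change.** 1. In every estradiol-level analysis, state where the level enters the model. Adjust for the pre-surgery value of the outcome, for route, and for DXA fat mass where the baseline scan preceded surgery (limited-participation women may have it up to a month afterwards). Do not rely on a regimen term as the repair, because the within-regimen slope is the confounded part.
2. Report the slope as an observational association, not as a dose response caused by estradiol level. Beside it, show the intention-to-treat difference in outcome and the arm difference in mean estradiol.
3. Optionally, as a sensitivity analysis, give the regimen-as-instrument slope with a weak-instrument-robust interval. State that it depends on the separation achieved and on regimen acting only through estradiol level. Agreement in direction between this slope and the association should not license causal wording: with no estradiol effect the two agree about half the time by chance.

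The cost is wording and a few lines of code on data already planned, a few degrees of freedom, and a more cautious Aim 2 conclusion. Conduct, sample size and the primary analysis are unchanged. Unmeasured confounding may remain, since absorption, metabolism and symptom-driven dosing are only partly captured by these covariates.
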